1 PROTOCOL SUMMARY

1.1 SYNOPSIS

Title:	Project EPIC Randomized Controlled Trial
Grant Number:	K76AG064327 (National Institute on Aging)
Study Description:	Project EPIC (Empowering People with Independence in COPD) is a multiphase study to advance the science of palliative care and geriatrics for people living with COPD and their caregivers. Embedded in Project EPIC is a multiphase intervention development program to refine and pilot test the EPIC early palliative care intervention in older adults with COPD and their caregivers informed by the ENABLE (Educate, Nurture, Advise Before Life Ends) model for early palliative care. EPIC is a 6-month early palliative care intervention that uses palliative care-trained nurse coach interventionists to deliver the Charting Your Course curriculum by phone to patients and their caregivers. In a formative evaluation, the EPIC intervention was refined to meet the needs older adults and their caregivers. This study seeks to summatively evaluate the refined EPIC intervention for feasibility and acceptability through a hybrid type-1, effectiveness-implementation pilot randomized controlled trial (RCT) of EPIC + usual COPD care (intervention) versus usual COPD care (control).
Aims:	Aim 1: Explore feasibility and acceptability of the EPIC intervention. Hypothesis 1. Participants can feasibly complete the EPIC intervention (>80% of intervention components completed) and will report high acceptability (primary outcome). Aim 2: Determine the feasibility of a hybrid-type 1 effectiveness-implementation trial in older adults with COPD and their caregivers. Hypothesis 2. It is feasible and not burdensome to recruit, randomize, retain, and survey older adults with COPD and their caregivers (primary outcome). Exploratory Aim: Explore mean and variance estimates on secondary outcomes to inform a fully-powered trial (secondary outcome). Primary outcome: Intervention and trial feasibility and acceptability Secondary outcomes: Life-Space mobility, quality of life, emotional symptoms, cognitive impairment, functional status, loneliness palliative care uptake, and caregiver burden
Outcomes:	30 older adults with COPD and 30 caregivers
Study Population:	Early Phase I
Phase:	
Enrollment Sites:	2 sites: Pulmonary Clinic at The Kirklin Clinic (University of Alabama at Birmingham, Birmingham, AL) (primary site) and Cooper Green Mercy Health Services-UAB Health Authority (Birmingham, AL)

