3 AIMS AND OUTCOMES

TRIAL OUTCOMES - SUMMATIVE EVALUATION	
RE-AIM Implementation Framework (Aims 1 & 2)	
Reach Trial feasibility	Rates of screening, enrollment, retention, reasons for exclusion and refusals, randomization, and attrition.
Adoption Intervention feasibility	Mean rates of completion of core EPIC components out of possible 10 for patients and 8 for caregivers. Feasibility: Overall average completion of ≥8 sessions for patients ≥6 sessions for caregivers .
Acceptability	Quantitative (Patients/Caregivers): Post-intervention survey on intervention acceptability. Acceptability: Overall average score ≥8 of 10. Qualitative (Patients/Caregivers): Post-intervention semi-structured, in-depth interviews by telephone to explore acceptability, barriers, facilitators, and survey burden.
Implementation Intervention fidelity	A random sample of 50% of palliative nurse coach sessions will be reviewed monthly using a rigorous fidelity checklist. Palliative nurse coaches who exhibit a pattern of non-adherence on three consecutive ratings will receive additional supervision and training.
Survey completion	Quantitative: Survey completion rates. Feasibility: ≥80% of participants complete all surveys
Define usual care arm	Review electronic medical record to capture elements of “usual COPD care”.
Maintenance	Nurse coaches check in monthly to reinforce EPIC. Interviews explore barriers to maintenance.
“Effectiveness” (Exploratory Aim; Secondary Outcomes at Baseline, 12 weeks, and 24 weeks, where indicated)	
Life-Space Mobility (Target Secondary Outcome; R01 outcome)	UAB Life Space Assessment (LSA) (Patients/Caregivers): 15-item measure of community mobility; frequency, distance, and independence of movement in the 4 weeks prior to administration; LSA<60 (restricted Life-Space mobility) Lower scores → more restricted; MCID=5 points ($\alpha=0.80$).
Quality of Life	Chronic Respiratory Questionnaire (Patients): 20-item measure of quality of life in COPD; domains of dyspnea , fatigue , emotional function , and mastery . Higher scores → better. MCID=0.5 ($\alpha=0.70$) PROMIS Global Health 10 (Patients/Caregivers): 10-item measure; physical and mental health domains; 9 questions rated on a 5-point Likert-scale, and 10th question rates pain on a scale of 0 to 10. Raw scores converted to standardized t-scores ranging from 0 to 100, with lower scores → worse QOL.

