6.1.2 SUMMARY OF PROTOCOL

Training of Study Team Members

The intervention requires two nurse coaches who are hired and trained by the PI and co-investigator, [name]. Advanced training specific to EPIC consists of independent readings, review of all intervention materials and the protocol, in-depth discussions on COPD and its management, and thorough review of the protocol. The PI will chair weekly nurse coach meetings to review progress and intervention receipt.

Enrollment Procedures.

All agreeable and eligible patient participants who consent to participate in the study complete an intake form that includes demographic data (all participants), clinical data (patients only), and symptom surveys (patients and caregivers). We are measuring Life-Space mobility, quality of life, caregiver burden, functional status, mood symptoms, loneliness, and cognitive impairment. If time allows for participants, baseline surveys will be completed immediately after consent. If time does not permit in the patient's schedule, the intake surveys will be completed by telephone at a mutually-agreed upon time. Agreeable and eligible caregivers who consent to participate in the study will also be provided a short intake form of their demographic and background information as well as intake symptom surveys. If the time does not permit in the caregiver's schedule, the intake surveys will be completed by telephone at a mutually agreed upon time.

Summary of Randomization Procedures.

Randomization will take place after the informed consent and intake are obtained from both the patient and the caregiver. We will randomize 30 patient-caregiver dyads in a 1:1 fashion to the study arms: 1) EPIC + usual care (n=15 dyads); and 2) usual care alone (n=15 dyads). A randomization table will be generated to allocate all 30 dyads to the study arms. Randomization procedures will be supervised by the biostatistician, [name] (Co-I and trial statistician) at UAB. The randomization scheme will be executed using an Excel randomization table and recorded in REDCap. The study coordinator will complete the randomization procedure and record study group in REDCap. The study coordinator will inform the usual group participants of their group assignment and will also alert the interventionists to initiate intervention activities with the intervention group participants.

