6.1.3 SUMMARY OF TRIAL PROCEDURES

Control Arm

The control arm of the study will be usual care for COPD in pulmonary clinic (**Table 1**) which includes symptom management, inhalers, advanced COPD therapies as needed, illness education, informal tobacco cessation counseling, supplemental oxygen testing, and referral to cardiopulmonary rehabilitation and other services as appropriate per the clinician.

Table 1. Control Arm Procedures and Timeline (Usual Care)					
Study Week	Type of Session	Investigator	Participant	Estimated Participant Time (minutes)	Description
1	In-person/ Phone	Coordinator	Patient + Caregiver	60	Study introduction, informed consent, intake surveys
2-24	N/a	N/a	Patient + Caregiver	N/a	Usual COPD care
12	Phone	Data Collector	Patient + Caregiver	60	Midpoint surveys
24	Phone	Data Collector	Patient + Caregiver	60	Exit surveys
24	Phone	Coordinator	Patient + Caregiver	30	Post-intervention acceptability survey Post-intervention feedback interview

Intervention Arm

Dyads randomized to the intervention arm will receive EPIC along with usual care (**Table 2**). EPIC includes weekly, telephone-based palliative care nurse coaching aided by the manualized curriculum, *“Charting Your Course (CYC): An Intervention for Patients with COPD and their Caregivers”*. This is followed by brief telephone follow-up calls monthly until study completion. Patient participants are also scheduled for a visit with the Supportive Care Clinic at The Kirklin Clinic, where trained clinicians complete a comprehensive palliative care assessment, virtually if preferred. Current intervention materials for EPIC and nurse coach CYC phone scripts are being edited and refined. Final copies of all intervention materials and phone scripts will be submitted as an amendment at a later date.

Table 2. Intervention Arm Procedures and Timeline (EPIC + Usual Care)					
Study Week	Type of Session	Investigator	Participant	Estimated Participant Time (minutes)	Description
1	In-person/ Phone	Coordinator	Patient + Caregiver	60	Study introduction; consent; intake surveys
2-12	In-person/ Virtual	N/A	Patient + Caregiver	60	Supportive Care Clinic visit; comprehensive palliative care assessment
3	Phone	Nurse coach	Patient + Caregiver	45	CYC Session 1: Problem solving
4	Phone	Nurse coach	Patient +	45	CYC Session 2: Self-care management

			Caregiver		
5	Phone	Nurse coach	Patient + Caregiver	45	CYC Session 3: Assessing, prioritizing, and managing symptoms

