Patient	COPE, Problem Solving	Self-care	Symptom Management	Communication, Support, Decision-Making	Life Review, Accomplishments	Forgiveness, Regrets, Creating a Legacy	Monthly Follow-Up (Telephone)
Caregiver	COPE, Problem Solving, Role	Self-care	Being a Partner in Symptom Management	Communication, Support, Decision-Making	Monthly Follow-Up (Telephone)		
Activities	Medications and Symptom List, Activity Log, Communicating with Providers Checklist, Ottawa Personal Decision Guide, and Advance Directive						

Each telephone session with the nurse coach begins by asking if the time is convenient for the participant, a reminder that the calls are audio-recorded for fidelity monitoring and quality assurance, and an assessment of the patient participant's level of distress using the National Comprehensive Cancer Network's Distress Thermometer included in the guidebooks. The nurse coach uses the telephone script to guide conversation with the participant. The nurse coach will call back monthly after completing the last CYC session to review any needs of the patient participant per the nurse coach telephone script and to assess maintenance of practices. Caregiver participants will separately complete 4 intervention telephone sessions using their own guidebook. Phone calls will be scheduled at a day and time that is convenient for the caregiver participant, and the nurse coach.

Post-intervention Interviews

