9 STATISTICAL CONSIDERATIONS

9.1 HYPOTHESES

Aim 1: Explore feasibility and acceptability of the EPIC intervention.

Hypothesis 1. Participants can feasibly complete the EPIC intervention (>80% of intervention components completed) and report high acceptability (*primary outcome*).

Aim 2: Determine the feasibility of a hybrid-type 1 effectiveness-implementation trial in older adults with COPD and their caregivers.

Hypothesis 2. It is feasible and not burdensome to recruit, randomize, retain, and survey older adults with COPD and their caregivers (*primary outcome*).

Exploratory Aim: Explore mean and variance estimates on Life-Space mobility by the UAB Life Space Assessment and other GeriPal outcomes to inform a fully-powered trial (*secondary outcome*).

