9.4.2 ANALYSIS OF THE PRIMARY ENDPOINT(S)

We will summatively evaluate EPIC using the RE-AIM (Reach, Effectiveness, Adoption, Implementation, and Maintenance) evaluation framework.

Reach: We will use REDCap to track rates of screening, eligibility, enrollment, reasons for non-consent of eligible participants, and drop out.

“Effectiveness”: We will measure several secondary GeriPal outcomes and will explore participant perspectives on the acceptability and impact of EPIC as well as barriers and facilitators to implementation. The PI will train the project coordinator to conduct post-intervention semi-structured in-depth interviews of patients and their caregivers by telephone using an interview protocol developed during our pilot trial. The separate patient and caregiver interviews will be audio-recorded and transcribed using Landmark Associates. The PI will review every five transcripts for quality assurance to review with the coordinator and for ongoing interview guide refinement. We will conduct a thematic analysis of transcripts using NVivo Software (Version 12, QSR International). Informed by a within- and across- case comparison approach, we will code the data using concepts introduced by participants. Emerging codes across cases will be operationally defined and entered into a formal codebook. Member checking will be ongoing as previous participant insights will be asked of future participants (e.g. “A number of participants have said X. What is your perspective on this issue?”). To corroborate findings and establish trustworthiness, the PI and co-investigators will examine the data collection and analysis monthly and provide critical feedback on the emerging codes. We will explore within and across coded texts to extract converging themes and reach consensus on themes.

Adoption: We will record completion of intervention components (CYC sessions, follow up call, advance directive, activities) in REDCap and tabulate intervention completion rates (# participants completing component). Consistent with our prior intervention development studies, ≥80% completion rates for intervention sessions will be considered as evidence of feasibility.

Implementation: Informed by our prior fidelity monitoring procedures, we will audio record all palliative care coach intervention sessions for fidelity monitoring and will quarterly review at least 50% of the recordings to ensure standardized intervention delivery and further training.

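### The Aim 1 intervention-feasibility cut-off is inconsistent: a caregiver mean of 6 of 8 sessions (75%) suffices in Section 3, but Hypothesis 1 requires more than 80% and Section 9.4.2 at least 80%

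*Combined protocol and SAP*

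**What the plan says.** Four places state when completion of EPIC counts as feasible.

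- **Section 3, Adoption row.** Mean completion is counted "out of possible 10 for patients and 8 for caregivers. Feasibility: Overall average completion of ≥8 sessions for patients ≥6 sessions for caregivers".
- **Section 1.1, Hypothesis 1.** "Participants can feasibly complete the EPIC intervention (>80% of intervention components completed) and will report high acceptability". This is labelled a primary outcome.
- **Section 9.1, Hypothesis 1.** The same threshold is repeated: "Participants can feasibly complete the EPIC intervention (>80% of intervention components completed) and report high acceptability".
- **Section 9.4.2, Adoption.** "≥80% completion rates for intervention sessions will be considered as evidence of feasibility". The sentence before it says that staff will record completion of "intervention components (CYC sessions, follow up call, advance directive, activities) in REDCap and tabulate intervention completion rates (# participants completing component").

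Only Section 3 treats patients and caregivers separately. No section gives a reason for a lower caregiver figure or says which statement governs. Section 6.1.2 fixes the size of the intervention arm: "EPIC + usual care (n=15 dyads").

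**The concern.** Section 4.1 says the trial is designed to find out whether EPIC is feasible and acceptable. The completion cut-off is what turns an observed rate into a statement that the intervention is, or is not, feasible. If the sections disagree, one set of caregiver data can support either statement, and the choice between them could be made after the data are seen. The signs differ too (strictly above 80% in Hypothesis 1, at least 80% in Section 9.4.2), so the patient criterion also conflicts at its boundary.

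**Working it through.** **Inputs**
- Denominators: 10 for patients, 8 for caregivers (Section 3).
- Section 3 cut-offs: mean of at least 8 and at least 6.
- Other cut-offs: above 80% (Sections 1.1 and 9.1); at least 80% (Section 9.4.2).
- EPIC arm: 15 dyads (Section 6.1.2). Section 4.1 gives 30 patients and 30 caregivers per arm, which does not fit the 30 dyads in total stated in the same section, so 15 is used.

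**Step 1. Convert the Section 3 cut-offs to percentages**
- Patients: 8/10 = 80%. This reproduces the Section 9.4.2 rule.
- Caregivers: 6/8 = 75%. This does not; 0.80 × 8 = 6.4.

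**Step 2. Express the rules as caregiver session totals**
- Possible sessions: 15 × 8 = 120.
- Section 3: 15 × 6 = 90 or more.
- At least 80%: 15 × 6.4 = 96 or more.
- Above 80%: 97 or more.

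Totals of 90 to 95 pass Section 3 and fail both 80% rules. A total of exactly 96 passes Section 9.4.2 and fails Hypothesis 1.

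**Step 3. The patient boundary**

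A patient mean of exactly 8.0 is 15 × 8 = 120 of 150, or 80.0%. It passes Sections 3 and 9.4.2 and fails the strict sign in Hypothesis 1.

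**Step 4. Does the Section 9.4.2 tabulation change the cut-off?**

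If the rate for each of the 8 caregiver sessions is (participants completing)/15, the average of the 8 rates is total/(15 × 8) = total/120 = (mean sessions)/8. An average of at least 80% is therefore again a mean of at least 6.4. Under averaging, the two metrics agree and only the threshold differs.

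**Step 5. Chance of passing, 15 caregivers**

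With independent sessions the total is binomial(120, p):

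| True rate p | P(total ≥ 90), mean ≥ 6.0 | P(total ≥ 96), mean ≥ 6.4 |
|---|---|---|
| 70% | 0.14 | 0.01 |
| 75% | 0.55 | 0.12 |
| 80% | 0.93 | 0.55 |
| 85% | 0.999 | 0.95 |

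Sessions within one caregiver are unlikely to be independent. With a beta-binomial count per person (8 sessions each, summed over 15 people) and p = 80%:

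| Assumed within-person correlation | Mean ≥ 6.0 | Mean ≥ 6.4 |
|---|---|---|
| 0.1 | 0.87 | 0.55 |
| 0.3 | 0.80 | 0.55 |
| 0.5 | 0.77 | 0.55 |

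The documents give no correlation; the range is an assumption.

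**The case against.** The best defence is that Section 3 is the role-specific form of a general 80% benchmark, with 6.4 rounded down to 6. That is possible, but the documents do not say so, and a mean need not be a whole number. The neighbouring benchmarks in Section 3 (patients 8 of 10, acceptability 8 of 10, surveys 80%) all sit at 80%, which leaves the caregiver figure as the exception.

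It can also be said that little depends on the cut-off. Completion rates will be tabulated, no test or stated progression rule uses the threshold, and the sample size rests on the precision of the LSA. A pass chance near one half when the true rate equals the cut-off is normal for any cut-off. All of this stands, and it limits the size of the point.

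Three stronger readings are tempting and are not supported.
- **Incompatible metrics.** A reader might infer that Section 9.4.2 requires every component to reach 80% of participants. It does not say that, and averaging its rates gives the Section 3 metric.
- **Items that cannot be counted.** A reader might infer that the 10 and the 8 exclude the clinic visit listed in Table 2 ("Supportive Care Clinic visit; comprehensive palliative care assessment") or the activities listed in Section 6.1.3 ("Medications and Symptom List, Activity Log, Communicating with Providers Checklist, Ottawa Personal Decision Guide, and Advance Directive"). The visit cannot be ruled out. The number of monthly calls is not stated: four calls give 6 + 4 = 10 and 4 + 4 = 8, but three calls plus the visit give 6 + 3 + 1 = 10 and 4 + 3 + 1 = 8. As for the activities, Section 9.4.2 records them, but its threshold sentence concerns sessions only.
- **Pooling.** A reader might judge patients and caregivers together. The only section that gives session counts separates them.

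**Conclusion.** The inconsistency is real and rests on the text alone: 75% for caregivers in Section 3, at least 80% in Section 9.4.2, and above 80% in Hypothesis 1. It affects the statement made about a primary outcome and should be corrected before analysis.

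Its reach is narrow. On the mean-session metric, the caregiver verdict changes only when observed completion is at least 75% and below 80%, plus the exact-80% boundary created by the two signs, which also applies to patients. The probabilities depend on 15 EPIC caregivers, a common completion rate across sessions and the assumed correlations; the conflict between cut-offs needs none of these. A reader might infer that the feasibility result would be uninterpretable. It would not be, because the rates themselves will be reported.

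**What to change.** Before the data are analysed, state one rule in Sections 1.1, 3, 9.1 and 9.4.2: the mean percentage of scheduled sessions completed among all participants randomised to EPIC, judged separately for patients and caregivers, with feasibility at 80% or more (at least 8.0 of 10 and at least 6.4 of 8). Alternatively, declare 75% as a caregiver-specific criterion in all four places and give the reason. Either way, use the same sign throughout and keep the per-component participant counts in Section 9.4.2 as descriptive.

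The cost is wording in four sections; Section 9.4.2 already has session completion recorded in REDCap. Choosing 80% makes the caregiver criterion harder to meet: at a true rate of 80% the chance of passing falls to 0.55, from 0.93 with independent sessions or from 0.87 to 0.77 under the assumed correlations. Keeping 75% means defending a lower bar for caregivers.

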4 STUDY DESIGN

4.1 OVERALL DESIGN

This hybrid type-1 effectiveness-implementation pilot RCT is designed to answer the question “Is EPIC feasible and acceptable in older adults with COPD and their caregivers?”. The primary aims are to assess implementation feasibility and acceptability (intervention and trial) over 24 weeks (*Aims 1 and 2*). We will also explore means and variance estimates of the secondary GeriPal outcomes to guide future R01 development (*Exploratory Aim*). We will recruit 30 dyads of older adults with moderate to very severe COPD (FEV₁ <80%) from pulmonary clinic and their caregivers. Half of the dyads will be randomized to EPIC + usual care (n=30 patients and n=30 caregivers). To reflect current clinical realities and uphold the pragmatic design, the other half of dyads (n=30 patients and n=30 caregivers) will be assigned to usual care alone (**see Section 1.2 for Design Schema**). Participants will complete assessments at enrollment (T1), week 12 (T2), and week 24 (T3). The T2 assessment captures the short-term outcomes of the most intensive part of the intervention. The T3 assessment will capture the long-term outcomes of the intervention. Assessments will be administered by phone and entered into the REDCap database system by a data collector blinded to study arm. For non-responders after 2 weeks, assessments will be additionally attempted by the data collector.

4.2 SCIENTIFIC RATIONALE FOR STUDY DESIGN

Guided by the NIH Stage Model for the Behavioral Health Interventions, this study implements a hybrid type-1 effectiveness-implementation pilot RCT trial in NIH Stage 1 of intervention generation and refinement. We determined that a usual care condition was the optimal comparator to best serve the aims of this pragmatic trial. We considered an alternative control condition with equal attention by telephone (i.e. attention control); however, this could threaten the pragmatic trial design that is meant to reflect clinical realities for older COPD patients. Part of the design consideration of Aim 2 is also to better define “usual care”. Usual COPD care at UAB consists of pulmonary clinic visits, illness education, medications (inhalers, nebulizers), vaccinations, advanced COPD therapies, imaging, treatment of COPD exacerbations, cardiopulmonary rehabilitation, and specialist referral. All of this is predominantly focused on the patient; no specific direct caregiver services exist to support their needs. To further examine and describe usual care, we collect information from participants in both conditions on accessed services. The information collected on secondary GeriPal outcomes will guide future R01 study and trial design.

